This study aims to validate W-SUDs as a digitally-delivered substance use disorder program through a fully-powered randomized control trial that will test the comparative efficacy of the mobile-app based substance use disorder program to reduce substance use relative to an education-only control condition, which has no cognitive behavioral therapy and the content is not delivered through a conversational user interface.

b) State what the Investigator(s) hope to learn from the study. Include an assessment of the importance of this new knowledge.

The COVID-19 pandemic introduced significant, unprecedented, and immediate psychological challenges to all, including individuals with substance use disorders (SUDs). The impact upon individuals with SUDs will be multifaceted and far reaching. In terms of physical health, experts postulate that individuals with SUDs may be at greater risk of mortality from COVID-19 given the variety of pre-existing physical health conditions this group has traditionally faced (i.e., COPD, cardiovascular disease, general poor respiratory health). In addition, the pandemic will beget significant emotional and psychiatric disruption from the multifaceted impact of the illness. Such responses may include large-scale grief, loneliness, fear, loss of life experiences, constrained

Title : Woebot for Substance Use Disorders Phase 2 RCT: Digitally Delivered Intervention for Reducing Problematic Substance Use (SU sIRB) Short name: Anchor Study

Approval Period: 03/17/2023 - 05/11/2023

or frank inability to work, financial instability, risk of contagion, overwhelmed hospitals, limited access to recovery programs and reduced or significantly changed mental health service provision from clinics.

Woebot for Substance Use Disorders (W-SUDs) is a 2 phase SBIR industry-academic partnership between Woebot Labs Inc. and Stanford University that aims to develop and evaluate the evidence of the novel digital therapeutic, delivered by an artificial intelligence (AI)-powered, automated conversational agent named Woebot which is embedded in the therapeutic W-SUDs.

Milestones for Phase I included the development (e.g., content and engineering) of W-SUDs and piloting its preliminary efficacy, feasibility and acceptability among n=101 individuals with SUD.

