3. Risk of treatment avoidance due to engagement with either of the randomized interventions. In both interventions it is explicitly stated that the service should not be used in place of traditional treatment. [REDACTED]

4. Risk of suicide: Woebot informs the participant that it is not designed for crisis service. [REDACTED]

Additionally, if anyone is developing or indicating serious thoughts about suicide or harming themselves, it is best practice to call 9-1-1 and/or go to the nearest ER.

d) Explain the point at which the experiment will terminate. If appropriate, include the standards for the termination of the participation of the individual participant Also discuss plans for ensuring necessary medical or professional intervention in the event of adverse effects to the participants.

IRB Modification 12/19/2022: The study will terminate once the 3-month period with all 400 eligible participants has been completed and the analyses run and submitted for publication.

Participants can refuse to participate at any time.

When we learn of a participant's adverse event, the team will report the adverse event and may follow up with the participant for additional information. Resources will be offered. The EOT and 12-week surveys includes questions that assess for SAEs. More details about adverse events are in section e.

e) Data Safety and Monitoring Plan (DSMP). See guidance on Data Safety and Monitoring.

A Data and Safety Monitoring Plan (DSMP) is required for studies that present Medium or High risk to participants. (See Overall Evaluation of Risk above). If Low Risk, a DSMP may not be necessary. Multi-site Phase III clinical trials funded by NIH require the DSM Plan to have a Data Safety

Title : Woebot for Substance Use Disorders Phase 2 RCT: Digitally Delivered Intervention for Reducing Problematic Substance Use (SU sIRB) Short name: Anchor Study

Approval Period: 03/17/2023 - 05/11/2023

Monitoring Board or Committee (DSMC or DSMB). The FDA recommends that all multi-site clinical trials that involve interventions that have potential for greater than minimal risk to study participants also have a DSMB or DSMC.

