The role of the DSMC or DSMB is to ensure the safety of participants by analyzing pooled data from all sites, and to oversee the validity and integrity of the data. Depending on the degree of risk and the complexity of the protocol, monitoring may be performed by an independent committee, a board (DSMC/DSMB), a sponsor's Data Safety Committee (DSC), a Medical Monitor, a sponsor's safety officer, or by the Protocol Director (PD).

Describe the following:

What type of data and/or events will be reviewed under the monitoring plan, e.g. adverse events, protocol deviations, aggregate data?

The Data Safety and Monitoring Plan will include Woebot's standard safety net protocol as well as a Data Safety and Monitoring Board overseen by Stanford University. Woebot's Safety Net Procedures Study informed consent will state that Woebot is not a crisis program designed to address active suicidal ideation or overdose.

[REDACTED]

To make sure that we do not miss any cases, we over detect, rather than under detect. In addition, we periodically check the data for true/false positive rates. Adverse Events We do not anticipate that the use of the interventions will increase risk as outlined above. In addition, there is a limited capacity to detect adverse events (such as overdose, suicide attempt or hospitalization related to substance use or other) unless explicitly voluntarily reported by the participant. In the case Stanford University and / or Woebot Labs becomes aware of an adverse event, the appropriate protocol, approved by the DSMB and Stanford University's Institutional Review Board, will be immediately implemented. This includes immediate notification of the IRB, DSMB, and NIH, and an immediate convening of the DSMB to discuss requisite follow-up steps.

Identify who will be responsible for Data and Safety Monitoring for this study, e.g. Stanford Cancer Institute DSMC, an independent monitoring committee, the sponsor, Stanford investigators independent of the study, the PD, or other person(s).

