To ensure the data protection and safety of research participants, Stanford University will serve as the Data Coordinating Center for the study under the coordination of [name]. They will convene a group of three to serve as an oversight board with professional expertise in the area of the study. [name] is an expert in the field of addiction and substance use, and [name] has experience in managing data protections in the context of randomized clinical trials.

Provide the scope and composition of the monitoring board, committee, or safety monitor, e.g., information about each member's relevant experience or area of expertise. If the Monitor is the Stanford Cancer Center DSMC or the PD, enter N/A.

DSMB's specific goals: • Review new or modifications to existing risk management protocols • Review procedures for maintaining confidentiality, data collection, management, and analyses • Review progress towards meeting enrollment goals • Recommend continuation, discontinuation, modification, or termination of a study based on emerging data (from the study and from the literature) and evaluation of risk/benefit ratios • Conduct annual reviews to determine whether patient safety has been adequately safeguarded • Review progress reports

Confirm that you will report Serious Adverse Events (SAEs), Suspected Unexpected Serious Adverse Reactions (SUSARs), or Unanticipated Problems (UPs) to the person or committee

Title : Woebot for Substance Use Disorders Phase 2 RCT: Digitally Delivered Intervention for Reducing Problematic Substance Use (SU sIRB) Short name: Anchor Study

Approval Period: 03/17/2023 - 05/11/2023

monitoring the study in accordance with Sponsor requirements and FDA regulations.

Yes.

If applicable, how frequently will the Monitoring Committee meet? Will the Monitoring Committee provide written recommendations about continuing the study to the Sponsor and IRB?

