The proposed study has a dissemination plan that encapsulates two important arenas: 1) ClinicalTrials.gov compliance and 2) Dissemination. ClinicalTrials.gov Compliance If the proposal is successfully awarded, the applicant will ensure that the trial's registration and results reporting procedures are thoroughly managed. The trial will be registered promptly upon receipt of the award and before the recruitment of human subjects. All informed consent documents will include specific and thorough statements referring to the posting on ClinicalTrials.gov. At the conclusion of the study and following analysis of the results, results will be reported as well, in compliance with the ClinicalTrials.gov procedures. Woebot Labs has a protocol in place outlining the importance and details of ensuring the ClinicalTrials.gov procedures are up to date. Dissemination of Research Both Stanford University and Woebot Labs will facilitate with the dissemination of research. They will collaborate on manuscript preparation and submission, as well as abstract submission and presentations at national and international scientific and technology-oriented conferences.

Select One:

The Protocol Director will be the only monitoring entity for this study.

Y This protocol will utilize a board, committee, or safety monitor as identified in question #2 above.

10. Benefits

a) **Describe the potential benefit(s) to be gained by the participants or by the acquisition of important knowledge which may benefit future participants, etc.**

When evaluating the risks and benefits of the proposed study, it is believed that risks are relatively minimal when compared to the potential therapeutic benefits that subjects are likely to receive. The benefits of receiving W-SUDs include potentially reducing substance abuse, acquiring practical psychotherapeutic skills (from cognitive behavioral therapy, motivational interviewing, dialectical behavior therapy, and mindfulness), and receiving psychoeducation about substance abuse. Participants who reduce substance

Title : Woebot for Substance Use Disorders Phase 2 RCT: Digitally Delivered Intervention for Reducing Problematic Substance Use (SU sIRB) Short name: Anchor Study

Approval Period: 03/17/2023 - 05/11/2023

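### The app safety net can find events in the W-SUDs arm only, so the source of each adverse event should be recorded and any by-arm safety display should separate the sources

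*Protocol*

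**What the plan says.** Three routes by which an adverse event can come to light are visible in the Protocol.

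- **In-app safety net.** Section 9(e): "The Data Safety and Monitoring Plan will include Woebot's standard safety net protocol". The description of how it works is redacted. The text after the redaction says "To make sure that we do not miss any cases, we over detect, rather than under detect" and adds that "we periodically check the data for true/false positive rates".
- **Survey questions.** Section 9(d): "The EOT and 12-week surveys includes questions that assess for SAEs". These go to both arms. Section 2(a) also schedules a 4-week survey, but no SAE questions are described for it.
- **Volunteered reports.** Section 9(e) concedes that "there is a limited capacity to detect adverse events" unless the participant reports them, and does not limit this remark to one arm.

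Section 1(a) says of the control condition that "the content is not delivered through a conversational user interface".

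Once either Stanford or Woebot Labs learns of an event, Section 9(e) sends it down a single notification pathway. The visible text describes no record of how the event was found. The board's listed tasks include recommending "termination of a study based on emerging data (from the study and from the literature) and evaluation of risk/benefit ratios", and after the trial "results will be reported as well, in compliance with the ClinicalTrials.gov procedures". The SAP's group comparisons cover primary and secondary outcomes, and it contains no adverse-event analysis.

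**The concern.** A by-arm event count compares safety fairly only if events have a similar chance of being found in each arm. Here one arm has an extra route, set to favour sensitivity over specificity, and the other has no equivalent. The gap is widest before week 8: no solicited channel is described for that period, so a control event surfaces only if volunteered, while a W-SUDs participant also has an app to disclose into.

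Two readers could be misled. The board weighs risk against benefit on emerging data, some of it from participants who have not yet reached week 8. Readers of the posted results may see events by arm with no sign of how they were found. An excess in W-SUDs could then reflect better detection, and a low count in control could reflect missed events. Efficacy analyses are not affected.

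**Working it through.** The documents give no event rate, detection sensitivity or false-positive rate, so there is no planned figure to reproduce. The check has two parts: which channels reach which arm, and how far a mixed count could move under stated assumptions.

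**Channels by arm**

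| Channel | W-SUDs | Control |
|---|---|---|
| SAE questions, weeks 8 and 12 (Section 9(d)) | yes | yes |
| Volunteered report (Section 9(e)) | yes | yes |
| In-app safety net (Section 9(e)) | yes | no chat interface (Section 1(a)) |

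The last entry holds in practice rather than absolutely: Section 2(a) foresees, and checks for, control participants using a Woebot app.

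**Inputs.** Total N is 400 (Section 8(a)). The allocation ratio is not stated, so 200 per arm is assumed. The following are also assumptions:

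- p, the true event rate, equal in both arms
- s, the share of events captured by survey
- a, the chance that the app finds an event the survey missed
- f, the share of W-SUDs participants carrying an uncorrected false flag

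**Formulas**

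- Control recorded rate: c = p × s
- W-SUDs recorded rate without false flags: w = p × [1 − (1 − s)(1 − a)]
- W-SUDs recorded rate with false flags: w + (1 − w) × f

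**1. No false flags, p = 3%, s = 0.70, a = 0.30 to 0.80**

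- True events per arm: 200 × 0.03 = 6. Found by survey: 6 × 0.70 = 4.2. Missed: 1.8.
- The app adds 1.8 × 0.30 = 0.54 to 1.8 × 0.80 = 1.44.
- Ratio: 4.74 / 4.2 = 1.13 to 5.64 / 4.2 = 1.34.

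**2. No false flags, p = 5%, wider range**

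- s = 0.9, a = 0.1: 9.1 versus 9.0 events, ratio 1.01.
- s = 0.5, a = 0.5: 7.5 versus 5.0 events, ratio 1.50.

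**3. Uncorrected false flags, p = 5%, s = 0.9 to 0.5, a = 0 to 0.5**

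- f = 2%: from (0.045 + 0.955 × 0.02) / 0.045 = 1.42 to (0.0375 + 0.9625 × 0.02) / 0.025 = 2.27.
- f = 5%: from (0.045 + 0.955 × 0.05) / 0.045 = 2.06 to (0.0375 + 0.9625 × 0.05) / 0.025 = 3.43.

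**4. The app adds no events and flags are adjudicated (a = 0, f = 0).** The ratio is 1.00.

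**5. Survey completion differs: 60% W-SUDs, 80% control, s = 0.9 among completers, f = 0**

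- Effective capture: 0.6 × 0.9 = 0.54 versus 0.8 × 0.9 = 0.72.
- a = 0: 0.54 / 0.72 = 0.75.
- a = 0.3: (1 − 0.46 × 0.7) / 0.72 = 0.678 / 0.72 = 0.94.

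The direction reverses.

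**6. Set against chance.** At the upper end of step 1, treating the counts as Poisson, the standard deviation of the difference is about √(4.2 + 5.64) = 3.1. The shift of 1.44 is under half of that.

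**7. Survey SAEs only.** With a = 0 and f = 0 by construction, the ratio is 1.00 if survey completion is equal by arm. With the completion rates in step 5 it is 0.75, so completion has to be shown with the comparison.

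**The case against.** A reader might infer that the app detects adverse events continuously and that pooling all sources will make W-SUDs look less safe than control. The documents do not support that reading, and the case against it is strong.

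- The over-detection sentence concerns cases that the visible text never defines. The mechanism is redacted, and the same section says that adverse events are hard to detect unless volunteered. Whether the safety net generates adverse-event records cannot be seen. **This stands.**
- No planned by-arm count mixes sources. The only pooling mentioned in Section 9(e) is of data from different sites, the SAP has no adverse-event analysis, and the board itself decides what data it wishes to review. **This stands:** the bias is conditional on a display that is not described. What remains is that nothing visible would prevent one.
- A source field may exist in the separate event-handling protocol that Section 9(e) says the board and the IRB approve, or in the redacted text. **This stands.** The point is only that the visible text describes none.
- True and false positives are checked periodically, and staff may follow up with the participant (Section 9(d)). **This stands in part:** it limits the scenarios in step 3, but no rule is visible for confirming a flag before it is counted.
- The effect may be small and could reverse. **This stands,** as steps 5 and 6 show. Phase I attrition was high (Section 1(b)), so unequal survey completion is a realistic worry.
- Restricting every comparison to survey SAEs would drop confirmed events in non-completers and volunteered reports from either arm. **This stands** and shapes the fix.

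**Conclusion.** The point holds in a conditional form. Ascertainment is unequal by design: one channel is in practice confined to W-SUDs, the solicited channel common to both arms operates only at weeks 8 and 12, and the visible text does not say how each event's source is kept. If by-arm counts for the board or the results posting mix these sources, they could be biased, most likely against W-SUDs.

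The size is unknown. Across the scenarios above, the recorded ratio at equal true rates runs from 0.75 to 1.50 without false flags and up to 3.43 if false flags in 5% of W-SUDs participants were counted uncorrected. All of this rests on assumed event, detection, false-flag and completion rates and on equal allocation. It shows how a mixed count could mislead and does not predict that it will. The change is worth making because it costs little and removes an avoidable ambiguity from any by-arm safety display.

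**What to change.** - **Protocol Section 9(e):** record the source of each event as survey item, in-app safety net, message to Woebot Labs, or other volunteered report. If the separate event-handling protocol already does this, refer to it.
- **Board report, results reporting and SAP:** in any by-arm safety display, present the identically asked week-8 and week-12 survey SAEs as the like-for-like comparison, with survey completion by arm.
- **Alongside it:** show all confirmed events by arm and source. List app-detected events separately as single-arm data, after true/false-positive review.

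The cost is one extra form field and one extra table. The like-for-like comparison leaves out events in people who did not complete the surveys, which is why all confirmed events are shown next to it. The handling of and response to individual events do not change.

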Title : Woebot for Substance Use Disorders Phase 2 RCT: Digitally Delivered Intervention for Reducing Problematic Substance Use (SU sIRB) Short name: Anchor Study

Approval Period: 03/17/2023 - 05/11/2023

be provided after randomization.

A debrief document is attached in Section 16 and will be provided to participants after their study period. For those who complete the final survey, it'll be provided by email soon after. For those who do not complete the final survey, the information will be provided by email a month after the final survey (at 12-weeks) is due. This is to allow sufficient opportunity for the final survey to be completed before the timing of the final survey is considered "late". No participant will be given the debrief after the intervention period at 8-weeks since the study will also be observing sustained change post-intervention (between 8-weeks and 12-weeks).

d) State if audio or video recording will occur. Describe what will become of the recording after use, e.g., shown at scientific meetings, erased. Describe the final disposition of the recordings.

No audio or video recordings will occur.

e) Describe alternative procedures or courses of treatment, if any, that might be advantageous to the participant. Describe potential risks and benefits associated with these. Any standard treatment that is being withheld must be disclosed in the consent process and form. (i.e. standard-of-care drug, different interventional procedure, no procedure or treatment, palliative care, other research studies).

Alternative Treatments for SUDSs include in-person individual and group forms of psychotherapy as well as Alcoholics Anonymous and Narcotics Anonymous.

All alternative options will be provided if she/he/they wishes to engage in an alternative treatment rather than the proposed study. However, given that previous Woebot study results are promising, the proposed line of treatments would appear to be appropriate and acceptable interventions for SUDs.

No standard treatment is being withheld.

f) Will it be possible to continue the more (most) appropriate therapy for the participant(s) after the conclusion of the study?

[figure not shown]
Yes

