Total duration for the research team is estimated to be 11 months. Content development is ready. Recruitment for about 5 months. Participation in the study is estimated to be 3 months. Estimated time for screening is around 5 minutes; Each survey estimated to be 15-30min. Study intervention is 8-weeks/2 months. Active participation is 3 months with follow up surveys at the 4- week, 8- week, and 12-week marks.

Data analysis is estimated to be 3 months.

9. Risks

a) For the following categories include a scientific estimate of the frequency, severity, and reversibility of potential risks. Wherever possible, include statistical incidence of complications and the mortality rate of proposed procedures. Where there has been insufficient time to accumulate significant data on risk, a statement to this effect should be included. (In describing these risks in the consent form to the participant it is helpful to use comparisons which are meaningful to persons unfamiliar with medical terminology.)

The risks of the Investigational devices.

N/A

The risks of the Investigational drugs. Information about risks can often be found in the Investigator's brochure.

N/A

The risks of the Commercially available drugs, reagents or chemicals. Information about risks can often be found in the package insert.

N/A

Title : Woebot for Substance Use Disorders Phase 2 RCT: Digitally Delivered Intervention for Reducing Problematic Substance Use (SU sIRB) Short name: Anchor Study

Approval Period: 03/17/2023 - 05/11/2023

The risks of the Procedures to be performed. Include all investigational, non-investigational and non-invasive procedures (e.g., surgery, blood draws, treadmill tests).

N/A

The risks of the Radioisotopes/radiation-producing machines (e.g., X-rays, CT scans, fluoroscopy) and associated risks.

N/A

The risks of the Physical well-being.

N/A

The risks of the Psychological well-being.

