Potential Upset due to Survey Questions: Foreseeable risks to subjects include the possibility that some assessment questions and/or treatment procedures may be upsetting to subjects. Experience at Stanford with similar populations has indicated that the risk of emotional upset during the assessments is low and if it occurred, the upset would likely not be serious in nature and temporary. Such risks will be minimized by the thoughtful selection of questionnaires. Potential participants will also be informed that they may drop out of the study at any time and if requested, appropriate treatment referrals would then be given.

There is possible risk of discomfort from losing access to the study intervention at the end of the 8-week period.

Possible risks of Woebot: Woebot is not intended to replace standard of care and should not be used in place of standard treatment.

Neither of the intervention groups are crisis services.

The risks of the Economic well-being.

N/A

The risks of the Social well-being.

Potential loss of confidentiality.

Overall evaluation of Risk.

Low - innocuous procedures such as phlebotomy, urine or stool collection, no therapeutic agent, or safe therapeutic agent such as the use of an FDA approved drug or device.

b) If you are conducting international research, describe the qualifications/preparations that enable you to both estimate and minimize risks to participants. Provide an explanation as to why the research must be completed at this location and complete the [LINKFORINTERNATIONALREASEARCHFORM] International Research Form. If not applicable, enter N/A.

N/A

c) Describe the planned procedures for protecting against and minimizing all potential risks. Include the means for monitoring to detect hazards to the participant (and/or to a potential fetus if applicable). Include steps to minimize risks to the confidentiality of identifiable information.

Given that the research aims to enroll a low-treatment seeking population, we do not envisage that participation in the study will be associated with elevated risk. We are not assessing suicidal ideation in our questionnaires. During the eligibility screener, those who have had a suicide attempt within the past year will be excluded from the study. It is not feasible to confirm the responses by participants to the questionnaires in real time. However, some risk is always present in studies that involve human participants. Such risk may include the following:

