[name] will coordinate the meetings by assisting in setting the agenda and ensuring that the necessary materials are provided for each meeting. The initial meeting of the Board will take place during the first three months of the study, i.e., before entry into the second Phase of the research, to allow for the consideration of the protocol from the viewpoint of data safety and participant confidentiality. Subsequent meetings will be held at 6-month intervals, with the possibility for either an interim meeting or telephone conversation conference call should the necessity arise. At the first meeting, [name] will brief the board on the study design and procedures. The Board will then provide feedback on the data that they will wish to review at their subsequent meetings.

Specify triggers or stopping rules that will dictate when the study will end, or when some action is required. If you specified this in Section 2g [Study Endpoints], earlier in this application enter 'See 2g'.

Endpoints will be indicated by the cessation of W-SUDs and educational intervention delivery at 8-weeks, the 12-week mark for WSUDs group (content will no longer be accessible), data analysis and interpretation, refinement of W-SUDs, and the end of the 3 month period (ending mark of the study).

Indicate to whom the data and safety monitoring person, board, or committee will disseminate the outcome of the review(s), e.g., to the IRB, the study sponsor, the investigator, or other officials, as appropriate.

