Woebot for Substance Use Disorders Phase 2 RCT: Digitally Delivered Intervention for
Reducing Problematic Substance Use

NCT ID: 04925570

March 17, 2023

Descriptive statistics (means, frequencies) will be run to describe the sample, and the balance achieved by the randomization, and to examine ratings of program feasibility and acceptability. Missing data on individual survey items is anticipated to be minimal. As needed, individual participants' average score values may be imputed when missing individual items on a scale (e.g., PHQ-8). For the outcomes of interest, the target estimand is the intent to treat on the study population with no loss to drop-out of the study (i.e., this estimand incorporates noncompliance with the randomization's assigned level of intervention). We will examine predictors of study retention. Generalized Linear Models (multivariable models) will test for group differences in changes in the primary outcome and secondary outcomes. The dependent variables will be baseline to EOT (and baseline to 1-month follow-up) change scores. The models are used to adjust for baseline group differences and will apply weights to adjust for correlates of study retention. Participant weights will be calculated as the inverse of predicted probability values from a logistic regression model predicting EOT (and 1-month follow-up) retention.

Between-subject differences in baseline variables may be substantial (e.g., baseline number of substance use occasions) so the models will use change from baseline to a given time point (e.g., number of substance use occasions at EOT minus the number of substance use occasions at baseline). This trial, while not an exact replication, extends previous work with a waitlist control where the primary outcome was the change in baseline to EOT in substance use occasions. Thus, we separately analyze changes (a) from baseline to EOT, and (b) from baseline to 1-month.

Correlations also will be examined between W-SUDs engagement metrics and change in primary and secondary outcomes in the treatment group. Additionally, a per-protocol analysis will be limited to treatment participants who use W-SUDs at least 4 of 8 weeks and control participants who view at least half of the online psychoeducational fact sheets.

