Bivariate correlations will examine associations between changes in substance use problems and changes in use occasions, confidence, depression, anxiety, and work productivity scores. Participants will be prompted to report craving within W-SUDs daily. If participants provide multiple craving ratings within a day, the scores will be averaged for that day. To examine changes over time in daily craving ratings, generalized estimating equation (GEE) linear models will be run with week entered as a factor, setting week 1 as the reference category.

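### Does it matter that the protocol leaves unclear whether W-SUDs content closes at week 8 or week 12?

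*Protocol*

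**What the plan says.** **When the intervention ends.** Protocol section 8(m) states "Study intervention is 8-weeks/2 months". Section 2(a) asks participants to take part in their assigned group for 8 weeks and places the last survey at 12 weeks, about 30 days after treatment. Section 2(g) takes that follow-up as the study endpoint, and section 8(k) labels the 8-week assessment as EOT.

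**When access ends.** Section 9(a), on psychological well-being, says: "There is possible risk of discomfort from losing access to the study intervention at the end of the 8-week period". Section 9(e), answering the form's question on triggers and stopping rules, lists "cessation of W-SUDs and educational intervention delivery at 8-weeks" and then, as a separate item, "the 12-week mark for WSUDs group (content will no longer be accessible". The same list goes on to data analysis, refinement of the program and the end of the 3-month period.

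**What week 12 is for.** Section 2(c) holds back the debrief until after the final survey because "the study will also be observing sustained change post-intervention (between 8-weeks and 12-weeks".

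**What the SAP does with it.** "we separately analyze changes (a) from baseline to EOT, and (b) from baseline to 1-month". The estimand is intent to treat and takes in noncompliance with the assigned intervention. The per-protocol set requires W-SUDs use in at least 4 weeks out of 8. Two other analyses use app data: "Correlations also will be examined between W-SUDs engagement metrics and change in primary and secondary outcomes in the treatment group", and a GEE model of daily craving ratings "with week entered as a factor, setting week 1 as the reference category". Neither names a last week.

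**The concern.** The item in section 9(e) names one arm and one later date, and it ties loss of content to that date. Read naturally, W-SUDs content stays open until week 12, which does not fit section 9(a). No other sentence in the supplied text says when the app is switched off.

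Two things would be at stake. First, if W-SUDs users kept the content in weeks 9 to 12, a difference at week 12 could reflect continued availability rather than persistence after withdrawal, and later access might differ between arms. Second, with no last week stated for the engagement metrics or the craving model, an analyst could include or leave out weeks 9 to 12 after seeing the data.

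**Working it through.** The plan has no figure of its own to reproduce here. The check is calendar arithmetic and a comparison of sections.

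**1. Timing of the final survey.** Week 8 is 8 × 7 = day 56. Week 12 is 12 × 7 = day 84. Thirty days after EOT is 56 + 30 = day 86. The protocol's two descriptions of the last survey (12 weeks, and 30 days after treatment) therefore agree to within 86 − 84 = 2 days.

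**2. What differs between the two readings.**

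| Quantity | Content closes at week 8 | Content closes at week 12 |
|---|---|---|
| Delivery ends | day 56 | day 56 |
| Possible content access | 56 days | 84 days (84/56 = 1.5 times) |
| Days from end of delivery to the week-12 survey | 84 − 56 = 28 | 84 − 56 = 28 |
| Days without access before that survey | 84 − 56 = 28 | 84 − 84 = 0 |

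Only access differs. Time since delivery ended is the same, so calling weeks 9 to 12 post-intervention, in the sense of after delivery, is correct on both readings.

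**3. Recall period.** The supplied text gives no recall window for the outcome measures. Assume 30 days. A day-84 survey then covers 28 of 30 days after delivery ended, and a day-86 survey covers 30 of 30, on either reading. Days after content closed would be 28 or 30 of 30 if it closed at week 8, and 0 or 2 of 30 if it closed at week 12. With an assumed window of 28 days or less, a day-84 survey lies wholly after delivery.

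**4. Effect on the two outcome contrasts.** Baseline to EOT ends at day 56, before the readings part. Baseline to 1 month compares groups as randomised, whatever they used. Neither the change scores, the retention weights nor the model depends on the access date. So 0 of 2 estimates change, and 1 of 2 is affected in how it may be described.

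**5. Effect on the craving model.** With week 1 as reference there are 8 − 1 = 7 week coefficients if data stop at week 8, and 12 − 1 = 11 if they run to week 12. Because week is a factor, later weeks add terms. Under an independence working correlation (an assumption, since the SAP names none), the coefficient for each of weeks 2 to 8 is that week's mean minus the week-1 mean, and extra weeks leave it unchanged. Under another working correlation it could shift with unbalanced data. The model has no control arm, and Protocol section 1(b) lists craving among the questions to be explored.

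**6. Effect on the engagement correlations.** App use after day 56 cannot influence change measured by day 56, so the sensible window for the EOT correlations is weeks 1 to 8. For 1-month change either window could be used and named in the table title. The only app-use window the SAP does state, in the per-protocol rule, is 8 weeks.

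**The case for a change.** The strongest case for acting is this. A W-SUDs-only mark at week 12 would be redundant if content had already closed at week 8, particularly as the end of the 3-month period appears separately in the same list. Section 2(g) makes the follow-up after treatment the study endpoint, and section 2(c) gives sustained change as a purpose of weeks 8 to 12. One sentence in the protocol and one in the SAP would remove the doubt cheaply, and analysis windows are better fixed before data are seen.

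Part of this stands. The two sentences do pull apart on the natural reading, and the supplied text does not settle the date. A report claiming that benefit persisted without the app would need to know it.

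The rest carries less weight. Section 9(e) is a loose list answering a form question on stopping rules. It includes program refinement and data analysis, so it is weak evidence of a deliberate 12-week access rule. It can also be read as saying that content is already closed by week 12, and then nothing conflicts. The form refers to an attached protocol, and section 2(a) promises instructions to each group; either may give the date. The phrase about sustained change explains when the debrief is sent. The SAP calls the time point only a 1-month follow-up and builds no durability claim on it. Nor are all the app-based analyses open-ended, since the per-protocol rule has its window.

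**Conclusion.** No change to the plan follows. The treatment period is stated consistently as 8 weeks; what is unclear is residual content access in weeks 9 to 12, a matter of 0 or 28 days without access before the final survey. That touches neither randomised estimate. It bears on one description only: whether the 1-month result may be called change without access to the content. Access is also not the same as use, and the documents do not allow the share of any week-12 difference due to later use to be computed.

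The missing last week in the engagement correlations and the craving model is a gap that analysts fill sensibly, guided by the 8-week treatment period and the 8-week per-protocol rule. A table of app use in weeks 9 to 12 would be optional, and it depends on logging after week 8 that the documents do not state.

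The sentences in sections 9(a) and 9(e) need to be reconciled by the study team as a matter of wording; this review takes no view on which date is right. The conclusion assumes that the report follows the SAP in presenting week 12 as a 1-month follow-up compared by assigned group, and that the engagement and craving results stay supportive.
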